1 AMENDMENT HISTORY

Amendment No.	Protocol Version No.	Date issued	Author(s) of changes	Details of Changes made
1	1.1		[name], Perf-Act BreCon Study Co-ordinator & [name]	Sections 5, 6, 10.2 and 12.2.2 revised to change the pain score collection for each breast to 18hr post-surgery and at Follow-ups week 1, week 2 and week 4-6.
				Section 5 updated to include an Overall Purpose of this study.
				Section 7 updated to include more information, explaining the relationship between the current study and the development of the new tool.
				Section 12.2.1 updated to provide further clarification on the surgical procedure and clarified the beginning of the surgery as the pre incision on table and the end of mastectomy as post mastectomy before wound closure.
				Section 15 updated with further clarification on the data capture system.
				Section 17.1 updated to include the direction of the one-sided t-test.
				Administrative clarification: previous version of the protocol there was a typo on the footer, it was given version 1.1, dated 11/Oct/2023 when it was intended to be version 1.0, dated 11/Oct/2023.
				This version 1.1, dated 18/Dec/2023 is considered the updated version of the protocol.

4 LIST OF ABBREVIATIONS

AE/AR	Adverse event/Adverse Reaction
ACT	Addenbrooke's Charitable Trust
	Patient Reported Outcome Measure designed to evaluate outcomes among women
BREAST-Q	undergoing different types of breast surgery
CCTU-CT	Cambridge Clinical Trials Unit – Cancer Theme
СІ	Chief Investigator
CTCAE	Common Terminology Criteria for Adverse Events
(e)CRF	(Electronic) Case Report Form
DIEP	Deep Inferior Epigastric Perforator
EU	European Union
GP	General Practitioner
GCP	Good Clinical Practice
GDPR	General Data Protection Regulation
HES	Hospital Episode Statistics
Hr(s)	Hour(s)
HRA	Health Research Authority
ICF	Informed Consent Form
ICG	Indocyanine Green
ID	Identification
ISF	Investigator Site File
LD	Latissimus Dorsi

MDT	Multi-Disciplinary Team
NCI	National Cancer Institute
NHS	National Health Service
NIHR	National Institute for Health and Care Research
PI	Principal Investigator
PIS	Participant Information Sheet
PROMS	Patient Reported Outcome Measures
R&D	Research and Development
RCT	Randomised Clinical Trial
REC	Research Ethics Committee
SoC	Standard of Care
SOPs	Standard Operating Procedures
SMG	Study Management Group
SPY-PHI	SPY Portable Handheld Imaging
	Intraoperative and surgeon-controlled fluorescence assessment software designed to
SPY-QP	Relative Values (%)
TMF	Trial Master File
TMG	Trial Management Group
UK	United Kingdom
ULN	Upper Normal Limit

5 SYNOPSIS

Study Title	PerfAct BreCon Study: A prospective case-control study to Compare Tissue Perf usion between Retr Act ors and non-retractors during Immediate Bre ast Re Con struction
Internal ref. no.	A096761
Study Design	Prospective case-control study
Study Participants	Women 18 years of age and over undergoing bilateral mastectomy with immediate reconstruction.
Planned Sample Size (if applicable)	A total of 30 evaluable participants
Follow-up duration (if applicable)	Up to 42 days
Planned Study Period	12-15 months
Overall Purpose of this study	To collect clinical evidence to demonstrate the difference in trauma caused to the breast tissues due to current surgical practices.
Primary Objective	To determine if there is a difference in blood perfusion (Relative Value %) in the breast where the non-retractor technique is used during surgery versus the breast where the retractor technique is used, in the same patient.
Secondary Objectives	To assess whether there are differences in the post-surgical complications, post-surgical recovery and post-surgical pain scores associated with the breast where the non-retractor technique is used during surgery, versus the breast where the retractor technique is used; in the same patient.
Exploratory Objectives	1. To evaluate the surgeons experience of each different operative technique, retractors and non-retractors.
	2. To assess the differences in overall operative times between the breast where the non-retractor technique is used during surgery, versus the breast where the retractor technique is used.
Primary endpoint	The relative difference (%) in blood perfusion between each breast in the same patient. Blood perfusion will be measured at 3 time-points (T1: baseline, T2: mid-point, T3: end) during the mastectomy procedure. The relative difference is defined as the difference, D, of Blood perfusion at T2-T1. The t-test will be applied on the between-breast difference on D.

Secondary endpoints	 Fo compare the following post-surgical outcomes, as associated with the preast where the retractor technique is used during surgery, versus the preast where the non-retractor technique is used, within the first 30 days post-surgery: Patient hospital re-admission, where applicable Patient hospital stay duration, where applicable Patient re-operation required, where applicable Patient reported post-surgery pain scores assessed at the following time points: 18hr, follow-up week 1, week 2 and week 4-6 Incidence, type and severity of surgery related adverse events, where applicable Comparison of patients pre- and post-surgery outcomes, as measured by Modules 7, 8, 9 and 14 of the BREAST-Q Recon version 2.0 guestionnaire. 			
Exploratory endpoints	 1. Comparison of surgeons self-reported scores of the following between retractor and non-retractor technique: Operative comfort Operative difficulty/complexity Operative visibility Safety of technique Physical demand of technique 2. Comparison of: Overall operative time in breast where the non-retractor technique is used, versus the breast where the retractor technique is used, in the same patient. Proportion of time before the retractor is used in the breast where non-retractor technique is employed. 			

6 STUDY FLOWCHART

Population: Women 18 years + with bilateral breast cancer or pathological gene mutation

7 BACKGROUND AND RATIONALE

In the UK, 55,000 cases of breast cancer are diagnosed every year. It will remain the commonest cancer in women until 2035 (1). Worldwide, two million new breast cancers were diagnosed in 2018 (2). Surgery remains the mainstay of breast cancer treatment, and any surgery associated adverse outcome affects a sizeable population.

Post-operative complications can delay chemo or radiotherapy (3) and potentially contribute to systemic cancer recurrence (4). This can also negatively impact patients psycho social status, besides adding to the existing burden on both primary (5) and secondary care resources such as staffing and beds (6).

In the UK, 35-40% (7) of breast cancer patients undergo mastectomy (~20,000), 40% of which (~8,000) undergo immediate breast reconstruction (3, 8). An NIHR-funded UK national audit (9) revealed that complication rates associated with mastectomy and immediate reconstructions remain high; with infection being the leading cause of patient re-admissions, potential re-operation and loss of the implant (25% infection, 18% re-admission, 18% re-operation, 9% implant loss rates respectively). In line with National Quality Standards, if just infection were to reduce from 25% of 8,000 reconstructions (n-2000) to below 10% (n-800), 1200 NHS patients annually would benefit from a reduction in this one complication.

Extrapolation of UK statistics (8, 9) to global data will need to be conservative since global reconstruction rates are likely lower than in the UK.

The vital component of mastectomy and immediate breast reconstruction is the viability of the preserved skin envelope (with a healthy blood supply) once the underlying breast tissue is excised (10, 11). Any trauma and compromise of skin vascularity can lead to complications such as infection, skin necrosis and reconstruction failure.

To reduce complications. different interventional methods in mastectomy and immediate breast reconstruction have been tried to prevent post-surgery infections, but none have been widely adopted. Attempted solutions have included the use of Nitro-glycerine (vasodilator) ointment that improves the vascularity to some extent but was not adopted in practice due to systemic side effects (12). A RCT compared the complication rates between standard electrocautery and high-frequency radiosurgery where the study found that both methods had equal complication rates of 23% (13). Another NIHR-funded RCT of patients (n=141) at higher risk of complications such as diabetes and smoking, showed 26% skin necrosis in heat preconditioned (pre-operative skin warming to increase skin blood flow) breast tissue, with 11% of the patients requiring surgical intervention. Conversely, the control group revealed 35% skin necrosis, with 17% needing reoperation (14). One technique that could help decrease post-surgery infection and potentially reduce patient re-admission and re-operation is using a gentle technique to lift the tissue.

Using a gentle technique to lift the soft tissue could decrease post-surgery infection and reduce patient re-admission and re-operation. To enable a clear view of the operative field during surgery, surgical tools called retractors are used to forcefully lift tissue to allow access for the surgeon. The forceful lift can contribute to tissue injury and consequent complications. Eighty per cent of breast surgeons believed that retractors were the leading cause of injury to breast skin during immediate reconstruction (15).

There is thus ample scientific literature on the association of retractors (hard metal instruments) with trauma to the soft tissue that surgeons have discussed in various publications as referenced. However, since there are no solutions, surgeons spread fingers apart to minimise trauma to the tissues.

The surgeon's non-dominant hand is spread apart (like a 'V'), and the dominant hand is used to operate the instruments in between the fingers of the 'V' as an alternative to the assistant pulling firmly on the skin (Figure 1). However, fingers get tired soon and/or cannot reach the depth of the surgical dissection field and then they have to resort back to retractors.

Figure 1: Left side panel shows pull by Retractor, right side panel show Finger dissection

Surgeons currently employ both intra-operative dissection techniques; therefore, this is not a new intervention; yet, importantly, there is no such novel study design known in the literature.

Therefore, CI with a team of engineers has been working on a device that surgeons can wear that will spread surgeons passively (without fatigue and trauma to their fingers) and at the same time, the extenders will increase reach where fingers can't. This will be an alternative to the retractors.

Whilst seeking funds for the development of the potential solution, it was suggested to gather some objective clinical evidence to demonstrate the difference in trauma caused to the tissues due to both of the existing surgical practices (retractors versus fingers-based).

This prospective case-control study represents an opportunity to compare tissue perfusion during breast mastectomy when using metal retractors versus fingers to lift the tissue. This study does not propose a new surgical technique or use a new instrument.

Differences in tissue perfusion between the two sides in the same patient (so there are no patient confounding factors) will help demonstrate the perceived problem objectively. The outcome of this study will establish the difference in trauma caused to the breast tissues due to current surgical practices, consequently, help improve intra-operative dissection techniques and reduce post-surgery infection and in addition, help to build an evidence-based case for the possible innovation of a new device to aid surgeons during this type of surgery.

In immediate breast reconstruction, the skin envelope with or without nipple must be preserved/spared (skin/nipple sparing mastectomy) after the removal of underlying breast tissue. However, mastectomy removes the dominant blood supply through the breast tissue, so the spared skin needs to survive on smaller blood vessels (capillary network) travelling along the skin's surface.

Tissue perfusion is the blood flow and oxygen supply to tissues, including the skin. Even brief periods of compromised perfusion to the tissue can lead to irreversible harm and complications. Currently tissue flap perfusion for mastectomies (simple, skin and nipple sparing), localised perforator flaps and larger pedicled (LD flap) or anastomotic (DIEP) flaps are assessed by reviewing capillary refill, warmth, and serial patient reviews. There are no additional methods for actual real-time visualisation of the tissue's vasculature.

This study will use Stryker's SPY-PHI handheld imager device to measure tissue perfusion. This device allows the surgical team to measure tissue perfusion in real-time during surgery. Following the intravenous injection of a licensed fluorescent Indocyanine Green (ICG) dye, the Stryker SPY-PHI device detects the circulating fluorescent dye. The equipment and dye are widely used in surgery already. Stryker's SPY-PHI has a SPY-QP mode assessment software that detects percentage perfusion allowing for quantifiable and objective comparison between the breasts as per the SPY-PHI technology brochure.

A study by Harless et al. (16) and per the SPY-PHI technology brochure, this device enables the surgeon to objectively evaluate tissue perfusion of mastectomy flaps and make real-time adjustments to breast reconstruction.

8 STUDY DESIGN AND METHODS

8.1 Statement of Design

Patients (n=30) undergoing bilateral mastectomy with immediate breast construction (n=60 breasts) will be invited to take part in this prospective case-control, multi-centre study.

Consenting patients will complete a pre-operative questionnaire and then undergo surgery. In the same patient during the same operative episode, sequential tissue perfusion measurements will be taken as follows:

- First, in the right breast use the finger dissection non-retractor technique for as long as possible before reverting to metal retractors
- Secondly, in the left breast using retractors only throughout the entire procedure

The sequential measurements taken in each breast will allow for the comparison of tissue perfusion between the two different skin lift techniques.

Patients will be blinded to the technique used in each breast.

Following surgery, patients will be followed in order to observe the patient's 30-day postoperative recovery period.

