12.2.1 Surgery Procedure

The mastectomy with immediate reconstruction will be undertaken as per usual local procedures. Consented patients will undergo surgery and have sequential intra-operative fluorescence imaging assessments on each breast, whereby a fluorescent Indocyanine Green (ICG) dye will be injected intravenously and then detected using the Stryker's SPY-PHI handheld imager device to provide tissue perfusion measurements. The ICG dye will be administered intravenously as a bolus injection at the recommended dose of 0.1-0.3mg/kg body weight as per the manufacturer's guidelines for tissue perfusion diagnostics detailed in the ICG dye SmPC.

Right breast (Non-Retractor Technique)

The operating surgeon will first conduct the mastectomy procedure in the right breast using the non-retractor (finger dissection) technique to lift the breast tissue.

At the beginning of the mastectomy procedure, (defined as pre-incision on table and referred to as time TR1), and once confirmed that the fluorescent imager is ready to use, working and in hand, the surgeon will request that the ICG dye injection be administered to the patient. Once the dye is visualised, two tissue perfusion relative values (%) and the time in HH: MM (24hr format) will be taken and recorded. The first value will be the worst tissue perfusion relative value (%) observed in the 10x10cm area surrounding the incision, and the second value will be the best tissue perfusion relative value (%) observed anywhere in the breast.

The surgeon will then commence the mastectomy procedure and continue with the nonretractor (finger dissection) technique for as long as is comfortably possible and until finger fatigue prevents using this technique any longer. At this time point (referred to as TR2), the process of the ICG dye injection and two tissue perfusion measurements will be repeated as described for TR1.

After time point TR2 the surgeon will complete the mastectomy procedure using retractors to lift the breast tissue and the final ICG dye injection and two tissue perfusion measurements

will be completed at the end of the mastectomy procedure (defined as post-mastectomy before wound closure and referred to as time TR3).

In summary, the surgeon will request that the ICG dye be administered to the patient, after confirming the fluorescent imager is ready to use, working and in hand at the following three time points:

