- TR1- beginning of mastectomy procedure, defined as pre-incision on table
- TR2- when the surgeon switches from finger dissection technique to metal retractors
- TR3- end of mastectomy, defined as post-mastectomy before wound closure

At each time point (TR1, TR2 & TR3), two tissue perfusion relative values (%) and the time in HH: MM (24hr format) will be taken and recorded. The first value will be the worst tissue perfusion relative value (%) observed in the 10x10cm area surrounding the incision, and the second value will be the best tissue perfusion relative value (%) observed anywhere in the breast.

Left Breast (Retractor Technique)

The operating surgeon will then conduct the mastectomy procedure in the left breast using metal retractors **only** from the beginning until the end of the procedure.

The surgeon will request that the ICG dye be administered to the patient, after confirming the fluorescent imager is ready to use, working and in hand at the following three time points:

- TL1- beginning of mastectomy procedure, defined as pre-incision on table
- **TL2** at the same time point that the surgeon switched from using fingers to metal retractors in the right breast (Time in mins = Right breast TR2 –Right breastTR1)

For example: If surgeon switched from the non-surgical (finger dissection) technique to retractors after 30 minutes in the right breast, then the tissue perfusion measurements in the left breast at time point TL2 will be taken 30 minutes after the beginning of the mastectomy procedure TL1 in the left breast.

• TL3- end of mastectomy, defined as post-mastectomy before wound closure

At each time point (TL1, TL2 & TL3), two tissue perfusion relative values (%) and the time in HH: MM (24hr format) will be taken and recorded. The first value will be the worst tissue perfusion relative value (%) observed in the 10x10cm area surrounding the incision. The second value will be the best tissue perfusion relative value (%) observed anywhere in the breast.

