26.2 Appendix 2: Surgeon Questionnaire

Question	Score for the right breast (Non- retractor technique)	Score for the left breast (Retractor technique)
1. How physically fatiguing was the procedure? (0–10 scale; 0—not at all demanding; 10— extremely demanding) (17)		
2. How complex was the procedure? (0–10 scale; 0—not at all complex; 10—extremely complex) (18)		
3. What was the degree of difficulty of the operation? (0-10 scale; 0-not at all difficult; 10-extremely difficult)(18)		
4. Compared to other mastectomies of this type, how difficult was this operation? (0–10 scale; 0– not at all difficult; 10—extremely difficult) (19)		
5. How difficult was visualization during the operation? (0–10 scale; 0—not at all difficult; 10— extremely difficult) (19)		
6. How fatigued were you at the end of the operation? (0-10 scale; 0-not at all fatigued; 10-extremely fatigued) (18)		
 7. What is your degree of satisfaction with the technique used to complete the surgery? (0–10 scale; 0—not at all satisfied; 10—extremely satisfied) (Original to this study) 		

8 . Rate your perception of the safety of each soft tissue lift technique to the soft tissue around the	
incision (0-10 scale; 0-not at all safe; 10-extremely safe) (Original to this study)

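### Finger dissection is always on the right breast and first, retractors always on the left and second, so the primary comparison cannot separate technique from a side or order effect on the T1-to-T2 change

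*Protocol*

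**What the plan says.** Section 8.1 of the protocol sets the allocation: "First, in the right breast use the finger dissection non-retractor technique for as long as possible before reverting to metal retractors", followed by "Secondly, in the left breast using retractors only throughout the entire procedure". Section 12.2.1 repeats it: "The operating surgeon will first conduct the mastectomy procedure in the right breast", and later "The operating surgeon will then conduct the mastectomy procedure in the left breast". The surgeon questionnaire in Appendix 2 (26.2) builds the same assignment into its columns, the first of which is headed "Score for the right breast (Non- retractor technique". Nothing in the protocol randomises, alternates or counterbalances side or order.

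The primary endpoint (Sections 10.1 and 17.2) is the change D = T2-T1 in each breast, with a t-test on the between-breast difference in D. Under Section 12.2.1, T2 in the right breast is the moment of the switch from fingers to retractors. T2 in the left breast is taken after the same elapsed time from its own baseline. Each measurement needs its own dye injection. At the right-breast T2, for example, "the process of the ICG dye injection and two tissue perfusion measurements will be repeated as described for TR1", so three injections precede the left-breast baseline.

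Section 7 describes the comparison as one made "in the same patient (so there are no patient confounding factors", and expects the result to establish a difference in trauma caused by surgical practice.

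**The concern.** A within-patient comparison removes what the two breasts share. It does not remove what differs systematically between them. Here the retractor breast is always the left one, and is always dissected later in the same anaesthetic after three earlier dye injections. If any of this changes how perfusion moves between T1 and T2, the effect enters the mean difference and is read as an effect of technique.

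More patients would estimate the same mixture more precisely. A statistical analysis plan cannot repair it either, because no patient has another combination of technique, side and order to adjust on. It has to be settled in the design, before data are collected.

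The per-breast pain scores, surgeon scores and operative times share the aliasing. The protocol plans no per-breast baseline for them, so for these outcomes even a constant side or order difference would remain.

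**Working it through.** **Inputs** (Section 17.1): difference 10, SD 25, one-sided significance level 10%, power 80%, n=30 evaluable patients.

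**Reproducing the plan's figure.**
- Paired comparison, normal approximation: n = ((z0.90 + z0.80) × SD/difference)² = ((1.2816 + 0.8416) × 25/10)² = 28.17, rounded up to 29.
- Exact noncentral t: power is 79.97% at n=29 and 81.0% at n=30, so 30 is the smallest n that reaches 80%.
- A two-sample calculation would need 57 per group and does not fit.

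The stated n therefore reproduces if 25 is the SD of the between-breast difference in D. That reading is used below.

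**What the test estimates.** Let d be D in the finger breast minus D in the retractor breast. Let τ be the technique effect, s the effect on D of being the right rather than the left breast, and o the effect on D of being first rather than second. Under the fixed rule every patient has

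mean(d) = τ + s + o.

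A constant difference in perfusion level between sides, or between first and second breast, cancels in T2-T1. Only effects on the change remain. They enter as one quantity, b = s + o, which the data cannot separate from τ.

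**Size for an assumed b.** The protocol gives no value, so a range is used.
- Standard error = 25/√30 = 4.56.
- Significance threshold = 1.311 × 4.564 = 5.99, so an observed difference of about 6.0 points is significant.
- Rejection probability = P(t with 29 df and noncentrality (τ + b)/4.564 exceeds 1.311).

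| Assumed size of b | False-positive rate if b favours right/first and τ = 0 | Power if b opposes and τ = 10 |
|---|---|---|
| 0 | 10.0% | 81.0% |
| 2.5 | 22.9% | 63.2% |
| 5 | 42.0% | 42.0% |

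The two entries in the last row agree because the net mean is 5 points in both cases (0 + 5 and 10 - 5).

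**After randomising side, finger-first kept.** Half the patients have mean τ + o + s and half τ + o - s. The overall mean is τ + o: the side effect cancels and the order effect does not. Without adjustment, s adds to the variance. With s = 5 the SD becomes √(625 + 25) = 25.5 and power for a net 10-point difference is 79.8%. With one term for side (28 df), power is 81.0%. The n of 30 does not need to change.

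**The case against.** The best defence is that the design already has two safeguards. Each breast is its own baseline, so a fixed difference between sides or a constant dye background drops out. The left-breast T2 is also matched to the right-breast T2 on elapsed time. Both are real and narrow the problem to effects on the change. They do not remove it.

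Finger-first also has a purpose: the switch time in the finger breast defines when T2 is taken in the other. That stands as a reason for the order. It gives no reason for always using the right breast.

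Several stronger readings are tempting but are not supported:
- A reader might infer that the protocol falsely claims freedom from all confounding. Section 7 claims it only for patient factors, which is fair for a within-patient comparison. The gap is that it goes on to attribute the difference to surgical practice without mentioning side or order.
- A reader might infer that false positives are inflated. Neither direction nor size is known, and loss of power is equally possible.
- A reader might blame surgeon handedness or carried-over finger fatigue. The protocol states neither the number of surgeons nor their handedness, and the right mastectomy is completed with retractors before the left begins.
- A reader might infer that a fixed rule defeats patient blinding. Section 8.1 says "Patients will be blinded to the technique used in each breast", and nothing in the protocol shows that this would fail.

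Finally, the study is described as non-interventional and evidence-gathering. That tempers expectations, but the protocol already dictates technique by breast and by sequence.

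**Conclusion.** The point holds for the T1-to-T2 change. With one allocation for all patients, the primary test compares right/first/finger with left/second/retractor, and a difference cannot be attributed to technique alone. No analysis of these data can undo that.

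The consequence is conditional. If a side or order effect of 2.5 or 5 points on D favours the right/first breast, the nominal 10% error rate becomes 23% or 42%. If it runs the other way, power for a true 10-point difference falls from 81% to 63% or 42%. These figures assume that 25 is the SD of the between-breast difference, and the effect sizes are illustrations not taken from the protocol. The sample size itself is not in question.

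**What to change.** - In Sections 8.1 and 12.2.1, replace the fixed right/left rule with a 1:1 random allocation, per patient, of which breast receives finger dissection, from a list held in REDCap.
- Keep the finger breast first, so that T2 in the retractor breast can still copy the elapsed time to the switch.
- Relabel the TR and TL time points and the Appendix 2 questionnaire columns by technique, and record the side.
- In Section 7 and in the conclusions, state that order remains aliased with technique, so a difference cannot be attributed to technique alone.

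The cost is a protocol amendment, a short allocation list and relabelled forms, with no added patients or procedures. The amendment should also address how random allocation fits the non-interventional description in Sections 11.5 and 12.3. The limitation is that order stays a residual confounder. Randomising order as well would remove it, but is optional: in retractor-first patients T2 could no longer be copied from the finger breast, and a pre-set T2 might fall after the switch to retractors and dilute the contrast.
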